#### 6.4 Dose and Administration

Patients will be assigned to IMP as described in Section 6.3.

At each dispensing visit (Table 1), patients will receive kit(s) comprising 4 bottles (see Table 2). Each bottle contains 70 film-coated tablets. Patients will be dispensed 1 or

2 IMP kits at dispensing visits, as described in the site operations manual, to ensure that the patient has sufficient IMP to last until the next scheduled visit.

IMP	Bottles for mor	ning dosing	Bottles for evening dosing	
	Bottle 1	Bottle 2	Bottle 3	Bottle 4
Setanaxib 1200 mg/day	Setanaxib	Setanaxib	Setanaxib	Placebo
	400 mg tablets	400 mg tablets	400 mg tablets	tablets
Setanaxib 1600 mg/day	Setanaxib	Setanaxib	Setanaxib	Setanaxib
	400 mg tablets	400 mg tablets	400 mg tablets	400 mg tablets
Placebo	Placebo	Placebo	Placebo	Placebo
	tablets	tablets	tablets	tablets

Table 2Investigational Medicinal Product Kits

Patients will take 4 tablets per day, 1 tablet from each bottle. Two tablets will be taken in the morning and 2 tablets will be taken in the evening (see Table 2), for 24 weeks.

- Patients allocated to setanaxib 1200 mg/day will self-administer 2 tablets of setanaxib 400 mg in the morning, 1 tablet of setanaxib 400 mg in the evening, and 1 tablet of placebo in the evening.
- Patients allocated to setanaxib 1600 mg/day will self-administer 2 tablets of setanaxib 400 mg in the morning and 2 tablets of setanaxib 400 mg in the evening.
- Patients allocated to placebo will self-administer 2 placebo tablets in the morning and 2 placebo tablets in the evening.

Patients will be instructed not to take their morning IMP dose on visit days until after the study assessments have been completed.

The tablets should be taken orally with food or up to 30 minutes after eating a meal. Each tablet should be taken separately and swallowed whole with water. The patients will be instructed to distribute their morning and evening doses as even as possible.

For BID administration, the dosage interval should be at least 4 hours. A missed morning dose can therefore be taken up until 4 hours prior to the evening dose. Patients will be provided with a patient IMP dosing card. Patients will be instructed to record the date and time of each tablet that they take on the dosing card straight after they have taken the tablet.

Patients will be reminded to bring the IMP (including any empty bottles and packaging) and the patient IMP dosing card with them to each study visit.

The IMP dosing card will be considered as a source document. Site personnel will record the date and time of the IMP dose prior to PK Visits in the eCRF.

## 6.4.1 Dose Modification

No dose modifications are permitted on a patient-basis in this study. Dose interruptions are required in case of DILI, anemia, and hypothyroidism, when the events meet the

criteria as defined in Appendix II, Section 5.3.2.2, and Section 5.3.2.3, respectively. Events that require permanent discontinuation of IMP are listed in Section 4.4.1.

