- Cardiac disorders: Patients with certain cardiac conduction abnormalities as well as patients with a second- or third-degree atrioventricular block will be excluded from the study. Patients included in the study will undergo regular monitoring for evidence of cardiac disorders by 12-lead ECGs. If the patient develops a QT prolongation (QTc Fridericia interval >450 milliseconds for males and >470 milliseconds for females), or an increase in QTc greater than 60 milliseconds from Baseline, whichever comes first, or if the patient develops other severe cardiac conditions per the Investigator's judgment, the IMP will be discontinued.
- Liver disorders (DILI): Patients with total bilirubin >2×ULN and/or plasma ALT and/or AST >3×ULN will be excluded from the study. Liver biochemistry tests will be regularly monitored during the study. As noted in Appendix II, if prespecified levels of AST, ALT, total bilirubin, or international normalized ratio (INR) are met during the study, IMP administration will be interrupted while the patient undergoes further evaluation.

Drug-induced liver injury (DILI), anemia, and hypothyroidism will be AEs of special interest ([AESIs], see Section 7.1.5) in this study and will be reported within 24 hours of the Investigator becoming aware of the event.

An Adjudication Committee will remain blinded to patient treatment assignment and will adjudicate the AESIs and the adverse clinical outcomes (see Section 5.4). An unblinded Independent Data Monitoring Committee (IDMC) will oversee the safety of participating patients. The IDMC will regularly review an aggregated list of events adjudicated by the Adjudication Committee (see Section 9.4).

The medications being taken by a patient will be carefully evaluated by the Investigator before the patient is enrolled into the study, and concomitant medications will be recorded throughout the study. The main routes of the primary metabolism of setanaxib appear to be UGT1A9 to GKT289993 (N-glucuronide) and via CYP3A4, principally to the main active metabolite GKT138184 (product of demethylation). Therefore, strong inhibitors and inducers of UGT1A9 or CYP3A4 may affect the plasma exposures of setanaxib. Setanaxib is a weak inhibitor of CYP2C9, CYP2C19 and OAT3.

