#### 17.2.1 Criteria for Close Monitoring of Liver Biochemistry and IMP Action

- A) For patients with ALT and/or AST <ULN at study start (Baseline Values), unless an alternative cause for the combination of laboratory abnormalities is immediately apparent (and documented) at the time of the laboratory test elevations in the opinion of the Investigator, close monitoring for sDILI (as described in Appendix II, Section 17.2.2) will be performed in patients with any of the following criteria (all confirmed by repeat testing):
  - a. ALT or AST  $>3 \times ULN$
  - b. Total bilirubin >2×ULN
  - c. INR >1.5 (except for patients on anticoagulant therapy)

- d. Clinical signs or symptoms that are, in the opinion of the Investigator, consistent with hepatitis (such as right upper quadrant discomfort, fever, fatigue, nausea, vomiting, jaundice, rash, or eosinophilia >5% provided the latter is in combination with any of the other criteria listed under A-a, b, c or d).
- B) For patients with ALT and/or AST between ≥ULN and <3×ULN at study start (Baseline Values), unless an alternative cause for the combination of laboratory abnormalities is immediately apparent at the time of the laboratory test elevations in the opinion of the Investigator (and documented), close observation for DILI (as described in Appendix II, Section 17.2.2) will be performed in patients with any of the following criteria (all confirmed by repeat testing):

  - a. ALT or AST >2×Baseline at any time (see Figure 2 for illustration)
  - b. Total bilirubin  $>2 \times ULN$
  - c. INR >1.5 (except for patients on anticoagulant therapy)
  - d. Clinical signs or symptoms that are, in the opinion of the Investigator, consistent with hepatitis (such as right upper quadrant discomfort, fever, fatigue, nausea, vomiting, jaundice, rash, or eosinophilia >5% provided the latter is in combination with any of the other criteria listed under A-a, b, c or d).

During the close monitoring period in A and B, IMP can be continued, unless:

[figure not shown]
- The patient is symptomatic in addition to having elevated laboratory parameters
- Close Monitoring is not possible
- Criteria C of Appendix II (see below) are met and no other cause for laboratory abnormalities is clinically apparent and documented by the Investigator in the study documents
- At the discretion of the Investigator

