- **C)** For patients meeting any of the following events, IMP will be discontinued when no other cause for the combination of laboratory abnormalities is immediately apparent:
  - a. ALT or AST  $>5 \times$  Baseline
  - b. ALT or AST  $>10 \times ULN$
  - c. ALT or AST >3×Baseline (see Figure 3 for illustration) with 1 or more of the following:
    - i. Total bilirubin >2×ULN

- ii. Total bilirubin >1.5×Baseline and >ULN
- iii. INR >1.5 (except for patients on anticoagulant therapy)
- iv. Appearance of clinical signs or symptoms that are, in the opinion of the Investigator, consistent with drug-induced hepatotoxicity
- d. ALT or AST >Baseline with any 2 or more of the following:
  - i. Total bilirubin >2×ULN or 1.5×Baseline
  - ii. INR>1.5 (except for patients on anticoagulant therapy)
  - iii. Appearance of clinical signs or symptoms that are, in the opinion of the Investigator, consistent with drug-induced hepatotoxicity

If the above criteria in **C** are met, the Investigator will instruct the patient to discontinue IMP administration and return to the study center within 2 days of receipt of the laboratory test results to undergo a retest and additional investigations (ie, close monitoring) to assess for sDILI. IMP cannot be reintroduced.

[figure not shown]
Any suspected or confirmed DILI event, defined as events meeting the criteria in A, B, or C above, will be closely monitored by the Investigator and the IDMC and reported to the Sponsor as an AESI following the same procedure as for SAEs.

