12.6.2 Adjudicated Events

The following adverse clinical outcomes will be adjudicated during the study:

- All-cause mortality/Death
- Variceal bleed
- Portal hypertension bleed
- Hepatic encephalopathy (West Haven criteria)
- Spontaneous bacterial peritonitis
- Uncontrolled ascites requiring treatment

Additionally, events that require IMP interruption (DILI, anemia and hypothyroidism) will also be adjudicated.

The proportion of subjects with adjudicated events in the above categories will be summarized in the SS. All subjects with adjudicated events will be listed.

An additional summary will be produced summarizing the proportion of subjects experience the following (not necessarily adjudicated) Safety events.

- progression to cirrhosis
- death (all-cause)
- liver transplant
- MELD ≥15 if the baseline MELD score was <12
- new onset ascites requiring treatment (diuretics or paracentesis),
- development of large varices if no varices at baseline,
- hospitalization due to a decompensatory event (for example, variceal bleeding, hepatic encephalopathy, spontaneous bacterial peritonitis)

If no such events are reported, this table will not be included.

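### Protocol Sections 1.3 and 6.4.1 call for interrupting IMP on Appendix II liver criteria, but Appendix II lets dosing continue under A/B and stops it for good under C

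*Protocol*

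**What the plan says.** Places that speak of interruption:

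- Protocol 6.4.1: "Dose interruptions are required in case of DILI, anemia, and hypothyroidism", on the criteria in Appendix II for DILI. No tier is named. The next sentence reads "Events that require permanent discontinuation of IMP are listed in Section 4.4.1".
- Protocol 1.3, Potential Risks, liver bullet: citing Appendix II, it says that if prespecified AST, ALT, total bilirubin or INR levels "are met during the study, IMP administration will be interrupted while the patient undergoes further evaluation". Again no tier is named.
- Appendix II: the titles of Figures 2 and 3 describe triggers to interrupt drug. The figures themselves are not in the text available.
- SAP 12.6.2: "events that require IMP interruption (DILI, anemia and hypothyroidism) will also be adjudicated". SAP 8.0 describes the committee's remit in similar terms.

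Places that state another action:

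- Protocol 17.2.1, Criteria A and B: "During the close monitoring period in A and B, IMP can be continued, unless" one of four exceptions applies. These are symptoms together with elevated laboratory values, close monitoring not being possible, Criteria C being met without another cause, or the Investigator's discretion.
- Protocol 17.2.1, Criteria C: "IMP will be discontinued when no other cause for the combination of laboratory abnormalities is immediately apparent", followed by "IMP cannot be reintroduced". Section 4.4.1 item 7 lists suspected DILI meeting Criteria C as a reason to discontinue.
- Protocol 17.2.2 item 4: a patient with symptoms as well as elevated laboratory values is to stop drug at once.

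Protocol 7.1.5 counts an event meeting A, B or C as a DILI event of special interest.

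**The concern.** Section 6.4.1 takes its trigger from Appendix II but states its own action and calls it required. Section 1.3 does much the same. If DILI means any of tiers A, B and C, as Section 7.1.5 says, a site working from 6.4.1 and a site working from 17.2.1 can treat the same A/B patient differently while each follows the protocol as written.

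This is first a safety-rule problem, but it also reaches the data. SAP 12.3.3 summarises interruptions, and SAP 10.7.4 counts adverse events leading to drug withdrawal. In Sensitivity Analysis #1 (SAP 12.5.2.2.1), treatment discontinuation defines the retrieved dropouts and the time-since-discontinuation covariates. With a target of 22 patients per arm, one patient classified differently is 1/22 = 4.5% of an arm.

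**Working it through.** There is no plan figure to reproduce. The check maps each stated action to each Appendix II tier.

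**Step 1. Can DILI in 6.4.1 be confined to one tier?** No. Section 7.1.5 and the close of 17.2.1 both treat A, B and C as DILI events, and 6.4.1 cites Appendix II as a whole.

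**Step 2. Is there a patient in A/B, with no exception, who is clearly outside C?** Yes. Take a tier B patient with baseline ALT below 3×ULN and a confirmed ALT between 2× and 3× Baseline, with normal bilirubin and INR and no symptoms.

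- B-a (above 2× Baseline): met.
- C-a (above 5× Baseline): not met.
- C-b (above 10×ULN): not met, because 3 × Baseline is below 3 × 3×ULN = 9×ULN.
- C-c (above 3× Baseline plus another finding): not met.
- C-d (above Baseline plus two of bilirubin, INR, symptoms): not met, with none of the three present.

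Assume close monitoring is possible and the Investigator does not choose to stop. Section 17.2.1 then permits dosing, while 6.4.1 requires interruption.

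**Step 3. Criteria C.** Section 4.4.1 item 7 and 17.2.1 both say discontinue, and 17.2.1 bars reintroduction. Section 1.3 says interrupt pending evaluation and gives no pointer to 4.4.1. Section 6.4.1 does give that pointer, so it conflicts only if its first sentence is read alone.

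**Step 4. Symptoms with elevated laboratory values, outside C.** Add symptoms to the Step 2 patient. C-d needs two findings and only one is present, so C is still not met. Section 17.2.2 item 4 stops drug, while 1.3 and 6.4.1 say interrupt. Item 7 of 4.4.1 does not cover the patient; another item, such as item 2 at the Investigator's discretion, might.

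| Event | Sections 1.3 / 6.4.1 | Appendix II text | Section 4.4.1 |
|---|---|---|---|
| A/B, no exception | Interrupt | May continue | Not listed |
| C, no other cause | 1.3: interrupt; 6.4.1: refers permanent stops to 4.4.1 | Stop, no restart | Item 7 |
| Symptoms plus elevated values, not C | Interrupt | Stop at once | Not listed unless another item applies |

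**Step 5. Comparison within the same sentence of 6.4.1.** The sections cited for anemia (5.3.2.2) and hypothyroidism (5.3.2.3) each contain an explicit interrupt, retest, and resume-or-stop sequence. The visible text cited for DILI does not.

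**The case against.** The strongest reply is that Appendix II governs. Section 5.3.2.1 sends sites there for the IMP action and names Section 4.4 and Appendix II as the home of the stopping criteria; Section 1.3 is benefit/risk narrative. This carries weight for Criteria C. It does not settle A/B: 6.4.1 is an operative section with its own required action, and no text says which section prevails.

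A second reply is that the interruption step may exist in Appendix II after all. Figures 2 and 3 are not shown, and two of the A/B exceptions (monitoring not possible, Investigator discretion) do not say whether the stop is temporary or permanent. That is fair, so the point is limited to the visible text and the figure titles. But 6.4.1 does not confine interruption to the exceptions, so the conflict for the patient in Step 2 remains.

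Several stronger readings are tempting but not supported:

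- A reader might infer three incompatible actions for one event. Continue and discontinue are tiers of a single graded rule, separated by the exception that "Criteria C of Appendix II (see below) are met and no other cause for laboratory abnormalities is clinically apparent". The conflict is two-way within each tier.
- A reader might infer that a Criteria C patient could be restarted under 6.4.1. That section has no restart step and points to 4.4.1.
- A reader might infer that the wording is left over from an amendment. The summary of changes describes superseded text and is not evidence here.
- A reader might infer that adjudicated DILI events will be lost. Protocol 7.1.5, 9.4.1 and 17.2.2 already send these events for adjudication, SAP 8.0 defers to Protocol 9.4.1, and SAP 12.6.2 names DILI outright. The SAP label is loose, and nothing more is shown.
- A reader might take the 4 liver-test SAEs in 4 patients (Section 1.1.4) as evidence of divergence. They were counted to 21 August 2023, before version 5.0 of 27 September 2023. No tier is given, and all four patients discontinued IMP.

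**Conclusion.** The inconsistency is real and should be corrected. It is firm for A/B patients with no exception. For Criteria C it is partial, resting mainly on Section 1.3. For symptomatic patients outside Criteria C it is a mismatch between 17.2.2 item 4, the interruption wording and the 4.4.1 list. The SAP point is a matter of wording only.

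No numerical size can be attached, since the documents give neither the number of patients per tier nor any instance of sites acting differently. The importance comes from its being a stopping rule for liver safety that all sites share. The conclusion rests on two assumptions: that DILI in 6.4.1 has the scope given in 7.1.5, and that the missing figures do not change the actions written in 17.2.1. It takes no view on which action is clinically right.

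**What to change.** Reconcile Protocol Sections 1.3, 4.4.1, 6.4.1 and Appendix II, including 17.2.2 item 4 and the titles of Figures 2 and 3, so that each criterion tier and each exception carries one stated IMP action and says whether it is temporary or permanent. Which action applies is for the sponsor to decide.

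In SAP 8.0 and 12.6.2, replace the label based on interruption with a reference to the AESI definition in Protocol 7.1.5.

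The cost is a clarification letter or amendment wording plus two SAP sentences. Sample size, the primary model and data collection are unaffected.

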## 6.4.2 Intervention After the End of the Study

Continued access to IMP is not planned beyond the completion of the study.

## 6.5 Precautions and/or Lifestyle Considerations

Patients will be asked to fast from 10 pm on the day prior to study visits until after the study procedures have been completed. In cases where the FibroScan® assessments are carried out on a different day than the study visit, refer to Section 5.2.2 for fasting instructions.

## 6.6 **Prior Medication**

The requirements regarding prior use of UDCA and second-line therapies for PBC, including OCA, fenofibrate, or bezafibrate, are provided in the inclusion criteria (Section 4.1). The recording requirements for prior medications are included in Section 6.7.

## Prohibited Medications

The following medications are prohibited within 3 months of Screening Visit 1, and during the study: oral and systemic corticosteroids, colchicine, mycophenolate mofetil, azathioprine, methotrexate, sulfasalazine, leflunomide, cyclophosphamide, valproate, or isoniazid. Note: nonsystemic corticosteroids, ie, topical/nasal/inhaled/other corticosteroids are allowed provided used in recommended doses, and up to 7 days of low doses up to up to 10 mg prednisone or equivalent of oral/parenteral corticosteroids are allowed.

Treatment with any investigational agent within 12 weeks of Screening Visit 1 or 5 half-lives of the IMP (if known) (whichever is longer) is prohibited, as is current enrollment in another interventional clinical study.

## 6.7 Concomitant Medication and Procedures

The use of a UDCA at a prescriptional dose is required during the study, unless the patient is intolerant to UDCA (see Inclusion Criterion 6). Second-line therapies for PBC, including OCA, fenofibrate, or bezafibrate, are also permitted during the study. For patients receiving these agents, all efforts should be made to maintain the dose of UDCA, OCA, and fenofibrate or bezafibrate stable during the Double-blind Treatment Period. The reasons for considering a dose change should be clearly documented in the study documentation. Patients should not start additional treatments for PBC after Randomization. If PBC treatments are started it will lead to IMP discontinuation. Dose modifications of concomitant PBC treatments initiated before Randomization do not require IMP discontinuation.

Patients will be instructed not to take their usual PBC medications on visit days until after the study assessments have been completed. Patients will be reminded to bring their medications for PBC with them to each study visit.

Regarding COVID-19 vaccination, as setanaxib does not have immunosuppressive properties based on nonclinical and clinical safety data, the Sponsor considers that study patients may undergo COVID-19 vaccination during the study.

#### Concomitant Medications to be Used with Caution

Setanaxib has been shown to be a weak inhibitor of OAT3, CYP2C9 and CYP2C19 in a clinical study. In addition, setanaxib inhibited BCRP and P-glycoprotein *in vitro*. This may result in increased exposures of applicable concomitant medications, and hence caution should be exercised with use of:

- Medications that are primarily eliminated through OAT3
- Sensitive CYP2C9 and CYP2C19 substrates that have a narrow therapeutic range such as warfarin and phenytoin (CYP2C9) and S-mephenytoin (CYP2C19)
- Sensitive substrates of BCRP and P-glycoprotein such as digoxin

*In vitro* data suggests that setanaxib is an inducer of CYP2B6. This may result in decreased exposures and therefore reduced efficacy of applicable concomitant medications, and hence caution should be exercised with use of:

• Sensitive CYP2B6 substrates, such as tamoxifen, valproic acid, and cyclophosphamide

#### Prohibited Concomitant Medications

The prohibited (prior) medications and devices listed in Section 6.6 are also prohibited during the Double-blind Treatment Period.

In addition, the following medications are prohibited during the Double-blind Treatment Period:

- Potent CYP3A4 inhibitors (itraconazole, lopinavir/itonavir, telaprevir, clarithromycin, ritonavir, ketoconazole, indinavir/ritonavir, conivaptan, and voriconazole)
- Potent UGT1A9 inhibitors and inducers: such as belumosudil, cannabidiol, cannabinol, deferasirox, diflunisal, eltrombopag, fosphenytoin/phenytoin, isavuconazole, medical cannabis, mefenamic acid, methylene blue, morniflumate, niflumic acid, perampanel, regorafenib, rifampicin, sorafenib, umifenovir)

If patients receive a prohibited medication, Investigators should consider if IMP administration should be temporarily interrupted or permanently discontinued. Additionally, if a patient has taken a prohibited medication (eg, short-term antifungal therapy) and the Investigator learns about it later, this might not lead to the permanent

discontinuation of IMP. In this case, there should be no signs of drug-drug interaction and continuation of IMP administration will be left to the Investigator's discretion.

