### **Pharmacokinetics**

The Phase 1 studies have characterized the clinical pharmacokinetics (PK), safety and tolerability profile of single and multiple ascending doses of setanaxib and the main active metabolite GKT138184 in healthy subjects.

No safety signals or dose-limiting toxicities have been identified up to a maximum single 1800 mg dose or repeated 800 mg twice daily (BID) dose (total daily dose of 1600 mg) for 10 consecutive days.

Potential food and drug interactions have been evaluated. Study GSN000310 assessed the effect of repeated setanaxib administration on the PK of selected cytochrome (CYP) 450 isoenzyme CYP2C9, CYP2C19 and CYP3A4 and transporter substrates, including for OAT1 and OAT3 (organic anion transporters).

Both setanaxib and its main active metabolite (GKT138184) exhibit approximate dose proportional PK across the dose ranges studied. Following both single and multiple dose administration of setanaxib across all doses studied, the main active metabolite exposure is consistently approximately 20% of the corresponding parent exposure. The PK for setanaxib and GKT138184 are similar.

Setanaxib is rapidly absorbed after oral administration (time to maximum concentration  $[t_{max}]$  between 0.5 and 3 h post dosing), with a tendency for later  $t_{max}$  for both capsules and tablets when setanaxib is administered under fed conditions. Setanaxib dosed in the fasted state is typified by higher inter-subject variability in maximum concentration and area under the curve (AUC). Following single-dose administration of setanaxib tablets, estimates of setanaxib elimination half-life ranged from approximately 8 to 14 h, and 9 to 12 h for the main active metabolite GKT138184. Modest accumulation of both setanaxib and GKT138184 were observed on repeated BID administration of the tablet

formulation (for 1200 and 1600 mg total daily doses), with steady state Day 8 exposures ranging from 2 to 30% higher than corresponding exposures on Day 1.

The main routes of the primary metabolism of setanaxib appear to be uridine 5'-diphospho-glucuronosyltransferase (UGT) 1A9 to GKT289993 (N-glucuronide) and via CYP3A4, principally to the main active metabolite GKT138184 (product of demethylation). Therefore, strong inhibitors and inducers of CYP3A4 and UGT1A9 may affect the plasma exposures of setanaxib.

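### Section 6.7 prohibits potent CYP3A4 inhibitors but not CYP3A4 inducers, although the protocol says both may affect setanaxib exposure

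*Protocol*

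**What the plan says.** Protocol Section 1.1.4 (Pharmacokinetics) names two main routes of primary metabolism for setanaxib: UGT1A9, and CYP3A4, which principally forms the main active metabolite GKT138184. It concludes that "strong inhibitors and inducers of CYP3A4 and UGT1A9 may affect the plasma exposures of setanaxib". Section 1.3 (Potential Risks) repeats the conclusion: "strong inhibitors and inducers of UGT1A9 or CYP3A4 may affect the plasma exposures of setanaxib".

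Section 6.7 (Prohibited Concomitant Medications) turns this into two bullets for the Double-blind Treatment Period. The first opens "Potent CYP3A4 inhibitors (itraconazole, lopinavir/itonavir, telaprevir, clarithromycin, ritonavir" and lists inhibitors only. The second opens "Potent UGT1A9 inhibitors and inducers: such as belumosudil" and covers both directions. Its examples include "eltrombopag, fosphenytoin/phenytoin, isavuconazole" and "perampanel, regorafenib, rifampicin, sorafenib, umifenovir".

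The same subsection says what follows if a listed drug is taken: "If patients receive a prohibited medication, Investigators should consider if IMP administration should be temporarily interrupted or permanently discontinued". Exclusion criterion 15 (Section 4.2) applies a 3-month look-back from Screening Visit 1 to the drugs prohibited in Sections 6.6 and 6.7. SAP Section 9.6.4 includes use of a prohibited medication that could have affected efficacy among the grounds that may remove a patient from the Per Protocol Set (PPS).

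**The concern.** The protocol gives one pharmacokinetic reason for restricting four classes of drug and then restricts three. It offers no reason for leaving out the fourth. Two adjacent bullets, one covering inhibitors and inducers and the other inhibitors alone, look more like an oversight than a decision.

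A site that follows Section 6.7 as written could enrol a patient on a strong CYP3A4 inducer, or let one be started, without breaching the list. Criterion 15, the prompt to consider interrupting IMP, and the prohibited-medication ground for PPS review would then not apply expressly. With 60 to 70 patients planned over 80 to 130 centres, decisions left to each site may not be uniform.

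Exposure matters in this trial. Section 3.2.1 explains that doses were raised because efficacy at 400 mg BID was considered insufficient. It also gives a safety margin of only 0.7 for GKT138184 at the top dose.

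**Working it through.** No sample size, power or alpha figure bears on this point, so there is no plan figure to reproduce. The check compares the sections.

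**Step 1: classes named against classes prohibited.**

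| Class that may affect setanaxib (Sections 1.1.4 and 1.3) | Prohibited as a class in Section 6.7? |
|---|---|
| CYP3A4 inhibitors | Yes, first bullet |
| CYP3A4 inducers | No |
| UGT1A9 inhibitors | Yes, second bullet |
| UGT1A9 inducers | Yes, second bullet |

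Four classes are named and three are prohibited.

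**Step 2: does another section close the gap?**
- Section 6.6 prohibits named drugs and drug groups. CYP3A4 inducers are not among them.
- The caution list in Section 6.7 deals only with what setanaxib may do to other drugs (through OAT3, CYP2C9, CYP2C19, BCRP, P-glycoprotein and CYP2B6). It does not address what other drugs may do to setanaxib.
- Criterion 15 only points back to Sections 6.6 and 6.7.
- The medication recording rules capture use but do not restrict it.

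None of these restricts CYP3A4 inducers as a class.

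**Step 3: what is already covered.** Rifampicin and fosphenytoin/phenytoin are named in the UGT1A9 bullet. That bullet's list is open-ended, so any other CYP3A4 inducer that is also a potent UGT1A9 modulator is caught. The gap is therefore strong CYP3A4 inducers that are not also UGT1A9 modulators. The documents do not say which drugs those are.

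**Step 4: what remains for an uncovered drug.** The Investigator evaluates medications before enrolment (Section 1.3), can exclude for a condition that could interfere with the study (criterion 24), and can end participation for data integrity (Section 4.4.2). The Medical Monitor should be contacted with medication questions (Section 6.7). These are real safeguards, but all are discretionary.

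**Step 5: can the effect be sized?** That would need the size of a CYP3A4 inducer interaction, CYP3A4's share of setanaxib clearance, and the change in GKT138184. The documents give none of these, so no exposure or ALP figure can be derived.

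**Side check: overlap between the caution and prohibited lists.** The caution list names seven drugs: warfarin, phenytoin, S-mephenytoin, digoxin, tamoxifen, valproic acid and cyclophosphamide. Section 6.6 prohibits cyclophosphamide and valproate (counted here as the same drug as valproic acid), and Section 6.7 prohibits phenytoin. That is 2 + 1 = 3 of 7. The express ban governs, so the overlap is editorial.

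**The case against.** The strongest reply is that the practical gap may be very small. Rifampicin and phenytoin are already banned, the UGT1A9 list is open-ended, and the protocol says only that inducers *may* affect exposure. The Investigator's Brochure, to which the protocol refers for further detail, is not among the documents. Medication changes are reviewed at the Week 16 and 20 calls and recorded at every visit. Even a ban is soft in effect: Section 6.7 asks Investigators to consider interruption, and the SAP says deviations may lead to PPS exclusion. The PPS analysis is supplementary and the PK analysis is descriptive. All of this stands, and it sets the severity. It does not explain why one of four identified classes was left out.

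Three stronger readings are tempting, and the documents support none of them.

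- *Induction acts like a dose cut.* Section 1.1.4 says that setanaxib and GKT138184 "exhibit approximate dose proportional PK across the dose ranges studied". A reader might infer that an inducer would take a patient back to the 800 mg/day level already judged insufficient. But a lower dose reduces parent and metabolite together, whereas CYP3A4 principally forms the active metabolite. Faster conversion could partly offset the loss of parent drug, or could raise the component with the 0.7 margin. The documents do not say which.
- *The loss of ALP effect can be estimated.* Any such figure would rest on an assumed fraction of effect lost and an assumed number of users. The documents supply neither.
- *An unlisted inducer triggers no safeguard at all.* Criterion 24 and the Investigator's other discretion remain. The PPS list in SAP Section 9.6.4 is not stated to be exhaustive, and the Protocol Deviation Guidance Document that defines important deviations is not available here. The claim that holds is narrower: the listed-drug safeguards do not apply expressly.

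**Conclusion.** The mismatch between Sections 1.1.4 and 1.3 and Section 6.7 is certain on the text. Strong CYP3A4 inducers that are not also UGT1A9 modulators are not prohibited as a class and are left to discretion. Severity is minor.

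The size cannot be quantified beyond the count of three classes out of four. That the primary Full Analysis Set result is unlikely to change is a judgement, resting on the assumption that few patients would take such a drug. The documents give no number of users. The SAP's primary estimand also keeps data after important protocol deviations under a treatment-policy strategy, so naming the class would not by itself remove those patients from the primary analysis. The benefit is consistent site conduct and clearer PPS and PK review for any patient affected.

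**What to change.** Change the first bullet under Prohibited Concomitant Medications in Section 6.7 to *Potent CYP3A4 inhibitors and inducers*, and add inducer examples chosen by the sponsor, since the documents list none under CYP3A4. Criterion 15, the IMP-interruption prompt and the prohibited-medication ground for PPS review then apply expressly, with no change to their own wording.

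Optional tidying: remove phenytoin, valproic acid and cyclophosphamide from the caution examples, leaving warfarin, S-mephenytoin, digoxin and tamoxifen.

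The cost is a wording change made by amendment (Section 12). No new procedure or data item is needed, because medication from 90 days before Screening Visit 1 to the EoT Visit is already recorded. The downside is that a few more patients may be excluded, or have IMP interrupted, in a trial already redesigned for slow enrolment.

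SAP Section 12.4 describes the blinded data review as already held, so amendment may no longer be possible. In that case, flag CYP3A4 inducer use from the recorded medications beside the setanaxib and GKT138184 concentrations, and carry the corrected wording into the next setanaxib protocol.
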